14.0 APPENDICES

APPENDIX I

CTCAE (Common Terminology Criteria for Adverse Events), version 4.03

The exact full criteria for toxicity assessment can be obtained at the NCI CTEP website at the following link:

http://evs.nci.nih.gov/ftp1/CTCAE/CTCAE_4.03_2010-06-14_QuickReference_8.5x11.pdf

APPENDIX II

Tumor assessment via RECIST Criteria, Guideline Version 1.1

<http://imaging.cancer.gov/clinicaltrials/imaging>

APPENDIX III

Tumor Assessment per Immune-Related Response Criteria

Immune-related Response Criteria (irRC) are derived from modified World Health Organization (mWHO) conventions. Assessments of lymph nodes are derived from current RECIST guidelines.

a.) Definitions of Measurable/non-Measurable Lesions

All measurable and non-measurable lesions should be assessed at the initial Screening/enrollment, at the defined tumor assessment time points (see Time and Events Schedule), and during regular maintenance. Additional assessments may be performed, as clinically indicated for suspicion of progression. The Investigator will base response to treatment using the irRC.

i.) Measurable Disease

Measurable non-lymph node disease is defined as lesions that can be accurately measured in 2 perpendicular Diameters. Size criteria is defined based on the properties of the CT scan

- Spiral CT, 0.5cm thickness slice: both diameters must be at least $\geq 1.0\text{cm}$
- For $> 0.5\text{cm}$ thickness slices: larger diameter $>2.0\text{cm}$; the other $> 1.0\text{cm}$

Lymph nodes are measurable only if CT slice thickness is $<0.5\text{cm}$. Size criteria are that the lymph node be at least 15 mm in short axis.

ii.) Non-Measurable Lesions

Non-measurable (evaluable) lesions are all other lesions, including one-dimensional measurable disease and small lesions (not meeting the above criteria), and any of the following:

- lesions occurring in a previously irradiated, extracranial area (unless they are documented as new lesions since the completion of radiation therapy),

bone lesions,
-leptomeningeal disease,
-ascites,
-effusion (pleural or pericardial)
-cystic lesions
-abdominal masses not histological confirmed

Lymph nodes with a short axis < 10 mm are considered not pathological, and are not measurable.

b.) Definitions of Index/non-Index Lesions

i.) Index Lesions

Measurable lesions, up to a maximum of 5 lesions per organ and ten lesions in total, must be identified as index lesions to be measured at Screening. The index lesions should be representative of all involved organs. In addition, index lesions must be selected based on their size (e.g., lesions with the longest diameters), their suitability for accurate repeat assessment by imaging techniques, and how representative they are of the subject's tumor burden. At Screening, a Sum of the Product Diameters (SPD) for all index lesions will be calculated and considered the baseline SPD. The baseline sum will be used as the reference point to determine the objective tumor response of the index lesions at tumor

assessment.

ii.) Non Index Lesions

Measurable lesions, other than index lesions, and all sites of non-measurable disease, will be identified as non-index lesions. Non-index lesions will be evaluated at the same assessment time points as the index lesions. *After the initial assessment, changes in non-index lesions will contribute only in the assessment of complete response.*

c.) Calculation of Sum of Product of Diameters (SPD)

Sum of Product of Diameters is an estimate of tumor burden. The 2 greatest perpendicular diameters are used to estimate the size of each tumor lesion. The SPD is calculated as the sum of the product of the diameters for index tumor lesions. Several variations of the SPD are identified for the purpose of classification of tumor responses.

i.) SPD at Baseline

The sum of the product of the diameters for all index lesions identified at baseline prior to treatment on Day 1.

ii.) SPD at tumor assessment

For every on-study tumor assessment collected per protocol or as clinically indicated, the SPD at tumor assessment will be calculated using tumor imaging scans. All index lesions and all new measurable lesions that have emerged after baseline will contribute to the SPD at tumor assessment (irSPD).

iii.) SPD at NADIR

For tumors that are assessed more than 1 time after baseline, the lowest value of the SPD (SPD Baseline or SPD at tumor assessment) is used to classify subsequent tumor assessments for each subject. The SPD at tumor assessment using the irRC for progressive disease incorporates the contribution of new measurable lesions. Each net percentage change in tumor burden per assessment using irRC accounts for the size and growth kinetics of both old and new lesions as they appear. In this study the irRC as defined by the Investigator will serve as the basis of key endpoints for efficacy analyses and guide clinical care.

APPENDIX IV

International Myeloma Working Group (IMWG) Uniform Response Criteria for Multiple Myeloma

http://myeloma.org/pdfs/IMWG_Response_criteria.pdf

APPENDIX V

KARNOFSKY PERFORMANCE SCALE

100 Normal; no complaints; no evidence of disease
90 Able to carry on normal activity; minor signs or symptoms of disease
80 Normal activity with effort; some sign or symptoms of disease
70 Cares for self; unable to carry on normal activity or do active work
60 Requires occasional assistance, but is able to care for most personal needs
50 Requires considerable assistance and frequent medical care
40 Disabled; requires special care and assistance
30 Severely disabled; hospitalization is indicated, although death not imminent
20 Very sick; hospitalization necessary; active support treatment is necessary
10 Moribund; fatal processes progressing rapidly
0 Dead

6. ECOG Performance Status

Grade	Description
0	Normal activity. Fully active, able to carry on all pre-disease performance without restriction.
1	Symptoms, but ambulatory. Restricted in physically strenuous activity, but ambulatory and able to carry out work of a light or sedentary nature (e.g., light housework, office work).
2	In bed <50% of the time. Ambulatory and capable of all self-care, but unable to carry out any work activities. Up and about more than 50% of waking hours.
3	In bed >50% of the time. Capable of only limited self-care, confined to bed or chair more than 50% of waking hours.
4	100% bedridden. Completely disabled. Cannot carry on any self-care. Totally confined to bed or chair.
5	Dead.

* As published in Am. J. Clin. Oncol.: *Okern, M.M., Creech, R.H., Tormey, D.C., Horton, J., Davis, T.E., McFadden, E.T., Carbone, P.P.: Toxicity And Response Criteria Of The Eastern Cooperative Oncology Group. Am J Clin Oncol 5:649-655, 1982.* The Eastern Cooperative Oncology Group, Robert Comis M.D., Group Chair.

APPENDIX VI

Inclusion Criteria:

- 1) ≥ 18 years old; ISS stage I-III multiple myeloma;
- 2) Able to give informed consent;
- 3) ECOG Performance Status between 0 and 1;
- 4) Relapsed and/or refractory myeloma;
- 5) ≥ 1 osseous and/or extra-osseous lesion that can be radiated;
- 6) Candidate for pembrolizumab (as determined by physician, and adequate organ function as noted in **Table 1**);
- 7) Candidate for radiotherapy (as determined by physician);
- 8) Measurable myeloma disease (**urine protein > 200 mg in 24 hr urine collection, serum free light chain ratio > 100 with an abnormal k/l ratio, serum M protein > 0.5 g/dl**) ; **12 patients of the 24 patients do not have to have measurable myeloma disease;**
- 9) Negative urine pregnancy test within 2 weeks for female subjects;

Female subject of childbearing potential should have a negative urine or serum pregnancy within 2 weeks prior to receiving the first dose of study medication. If the urine test is positive or cannot be confirmed as negative, a serum pregnancy test will be required.

1. Female subjects of childbearing potential should be willing to use 2 methods of birth control or be surgically sterile, or abstain from heterosexual activity for the course of the study through 120 days after the last dose of study medication. Subjects of childbearing potential are those who have not been surgically sterilized or have not been free from menses for > 1 year.
2. Male subjects should agree to use an adequate method of contraception starting with the first dose of study therapy through 120 days after the last dose of study therapy.
3. Abstinence is acceptable, if this is the usual life style and preferred contraception for the patient.

Exclusion Criteria:

- 1) Previous anti-PD1 or anti-PD-L1;
- 2) Solitary plasmacytoma;
- 3) Smoldering (asymptomatic) multiple myeloma;
- 4) Currently participating and receiving study therapy or has participated in a study of an investigational agent and received study therapy or used an investigational device within 4 weeks of the first dose of treatment;
- 5) Has a diagnosis of immunodeficiency;
- 6) Known history of active TB (Bacillus Tuberculosis);
- 7) Hypersensitivity to pembrolizumab or any of its recipients;
- 8) Known additional malignancy that is progressing or requires active treatment (exceptions include basal cell carcinoma of the skin or squamous cell carcinoma of the skin);
- 9) Has active autoimmune disease that has required systemic treatment in the past 2 years (i.e. with use of disease modifying agents, corticosteroids or immunosuppressive drugs);
- 10) Known history of, or any evidence of active, non-infectious pneumonitis;
- 11) Active infection requiring systemic therapy;
- 12) Is pregnant or breastfeeding, or expecting to conceive or father children within the projected duration of the trial, starting with the pre-screening or screening visit through 120 days after the last dose of trial treatment.
- 13) Has a known history of Human Immunodeficiency Virus (HIV) (HIV 1/2 antibodies).
- 14) Has known active Hepatitis B (e.g., HBsAg reactive) or Hepatitis C (e.g., HCV RNA [qualitative] is detected).
- 15) Has received a live vaccine within 30 days of planned start of study therapy.

Note: Seasonal influenza vaccines for injection are generally inactivated flu vaccines and are allowed; however intranasal influenza vaccines (e.g., Flu-Mist®) are live attenuated vaccines, and are not allowed.

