1. PROTOCOL SUMMARY

Abbreviated Title	Pilot Study of Pembrolizumab and Single-fraction, Low-dose, Radiation Therapy in Patients with Relapsed or Refractory Multiple Myeloma
Trial Phase	Pilot Study
Clinical Indication	Relapsed or Refractory Multiple Myeloma
Trial Type	Pilot study
Type of control	None
Route of administration	Patients will receive on day 1, cycle 1 , radiotherapy (8 Gy/1fx) to an extra-osseous or osseous myeloma site followed by pembrolizumab (200 mg/kg i.v. on day 2 or 3 , then every 3 weeks +/- 7 days).
Trial Blinding	N/A
Number of trial subjects	24 patients (20 patients minimum, with 4 extra patients to account for loss to follow-up/attrition and/or failure to comply with recommended treatments); 12 patients will be allowed to not have measurable myeloma disease.
Estimated enrollment period	2 years
Description of enrollment	Following evaluation by medical oncology and radiation oncology, patients will be enrolled. Baseline assessment prior to enrollment may include bone marrow biopsy, peripheral blood collection, and staging of the patient per standard of care. Baseline serum and urine paraprotein analysis, bone marrow biopsy, PET/CT imaging, routine blood work, and baseline physical exam prior to enrollment. Patient with measurable myeloma disease will be screened for tolerability to Pembrolizumab and radiotherapy. Patients will be assessed at 1st month and every 3 month for response using the standard International Myeloma Working Group (IMWG) Response Criteria, and will undergo routine myeloma labs every 6 weeks until progression or as clinically indicated ; Patients with stable disease or better per IMWG response criteria will continue with maintenance pembrolizumab (200 mg/kg every 3 weeks for 2 yrs) . Patients that have progressive disease, or relapse after a complete response will be removed from the trial and treated per standard of care at the discretion of the treating physician.
Duration of Intervention	At least 24 months of Pembrolizumab, or until progression.
Duration of Evaluation	3 year (2 yrs for accrual, and at least 1 year follow-up for the last patient accrued on the study)
Estimated duration of trial	3 years (2 years to accrue + 1 years to follow all patients)
Duration of Participation	3 years
Study Center	Emory University. Atlanta, Georgia.

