Baseline work-up (per NCCN guideline) within 28 days +/- 14 days prior to enrollment: CBC with Diff, CMP, Calcium, Albumin, Serum Protein analysis, Quantitative Immunoglobulin, Serum Immunofixation (SIFE), 24 hr urine total protein, Urine Immunofixation, Serum Free Light Chain, Bone Marrow Biopsy (with IHC, flow, cytogenetics, FISH),

Whole Body PET/CT, Biopsy of Osseous or extra-osseous site (only if clinically indicated);
Pregnancy test;

Inclusion Criteria:

- 1) ≥ 18 years old; ISS stage I-III multiple myeloma that has progressive, relapsed, or refractory disease;
- 2) Able to give informed consent;
- 3) ECOG 0-1;
- 4) Relapsed and/or refractory myeloma; There is no minimum or maximum number of previous therapies that a patient may have received previously before being put on the current trial.
- 5) ≥ 1 osseous and/or extra-osseous lesion that can be radiated;
- 6) Candidate for pembrolizumab (as determined by physician, and adequate organ function as noted in **Table 1**);
- 7) Candidate for radiotherapy (as determined by treatment physician); These patients can have symptomatic disease and/or asymptomatic disease. A minimum of one site of radiation is required to any osseous and/or any extra-osseous disease. Radiation to any bony parts of the Head and Neck, Skull, Spine, ribs, and/or extremities are allowed. Radiation to any bony part for documented lytic disease is allowed. Radiation to any soft tissue plasmacytoma (including osseous and extra-osseous plasmacytoma) is allowed. The only exclusion criteria for radiation, is CNS metastases (see exclusion criteria # 16);
- 8) Measurable myeloma disease (**urine protein > 200 mg in 24 hr urine collection, serum free light chain ratio > 100 with an abnormal k/l ratio, serum M protein > 0.5 g/dl**) ; **12 of the 24 patients do not have to have measurable disease;**
- 9) Negative urine pregnancy test within 2 weeks for female subjects;

Female subjects of childbearing potential should have a negative urine or serum pregnancy within 72 hours prior to receiving the first dose of study medication. If the urine test is positive or cannot be confirmed as negative, a serum pregnancy test will be required.

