5. ADMINISTRATION OF STUDY PHARMACEUTICAL

In 2015, FDA approved Pembrolizumab (Keytruda) for the treatment of advanced melanoma and NSCLC patients; Pembrolizumab is a monoclonal antibody that targets the PD-1 receptor. Programmed death 1 (PD-1) (or CD279) is part of the CD28 family of proteins, which includes CTLA-4 and ICOS, that regulate T cell activity. PD-1 is a glycoprotein receptor that can be expressed on the surface of T cells, B cells and myeloid cells (monocytes and dendritic cells). In T cells, PD-1 expression is primarily induced by T cell receptor (TCR) engagement and ligation with PD-L1 and PD-L2, expressed on antigen presenting cells, and induces an inhibitory signal that antagonizes TCR signaling and other important pathways necessary for optimal T cell activation. Clinical trials with Pembrolizumab in advanced melanoma and NSCLC patients lead to approval by the FDA. Some efficacy in combination with lenalidomide for multiple myeloma has also been recently demonstrated. The recommended dose of Keytruda is 2mg/kg administered as IV infusion over 30 minutes every 3 weeks until disease progression, or unacceptable toxicity. Alternative dosing regimens are also available. The dose used on the Keynote -023 trial was 200 mg.

Dose Selection

Patients will receive pembrolizumab 200 mg IV delivered over a 30-minute period every 3 weeks until 2 years, or until disease progression, and/or unacceptable toxicity at the discretion of the treating physician. Infusions should be given over 30 minutes (not bolus or IV push).

Timing of Pembrolizumab Administration

Trial treatment should be administered on **Day 2 or 3 and then every 3 weeks +/- 7 days** after that as outlined in the Trial Flow Chart;

All trial treatments will be administered on an outpatient basis.

Pembrolizumab 200 mg will be administered as a 30 minute IV infusion every 3 weeks. Sites should make every effort to target infusion timing to be as close to 30 minutes as possible. However, given the variability of infusion pumps from site to site, a window of -5 minutes and +10 minutes is permitted (i.e., infusion time is 30 minutes: -5 min/+10 min).

The Pharmacy Manual contains specific instructions for the preparation of the pembrolizumab infusion fluid and administration of infusion solution.

Trial Blinding/Masking

This is an open-label trial; therefore, the Sponsor, investigator and subject will know the treatment administered.

Randomization Allocation

Not applicable

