It is unknown whether pembrolizumab is excreted in human milk. Since many drugs are excreted in human milk, and because of the potential for serious adverse reactions in the nursing infant, subjects who are breast-feeding are not eligible for enrollment.

Subject Withdrawal/Discontinuation Criteria

Subjects may withdraw consent at any time for any reason or be dropped from the trial at the discretion of the investigator should any untoward effect occur. In addition, a subject may be withdrawn by the sponsor-investigator if enrollment into the trial is inappropriate, the trial plan is violated, or for administrative and/or other safety reasons.

A subject must be discontinued from the trial for any of the following reasons:

8. The subject or legal or legal representative (such as a parent or legal guardian) withdraws consent.
9. Confirmed extra- extra-cranial radiographic disease progression.
10. Unacceptable adverse experiences as described in section 6 and 7.
11. Intercurrent illness that prevents further administration of treatment.
12. Investigator's decision to withdraw the subject.
13. The subject has a confirmed positive serum pregnancy test.
14. Noncompliance with trial treatment or procedure requirements.
15. The subject is lost to follow-up.
16. Completed at least 24 months of uninterrupted treatment with pembrolizumab or 35 administrations of study medication, or whichever occurs last;

Note: 24 months of study medication is calculated from the date of first dose. Subjects who stop pembrolizumab after 24 months may be eligible for up to one year of additional study treatment at the discretion of their treating physician, especially if their disease is clinically stable;

17. Administrative reasons
18. Confirmed radiographic disease progression per RECIST criteria
 1. *Note: A subject may be granted an exception to continue on treatment with confirmed radiographic progression if clinically stable or clinically improved, please see Section 6 and 7.*

The End of Treatment and Follow-up visit procedures are listed in Section 10 (Protocol Flow Chart) and Section 11. After the end of treatment, each subject will be followed for 30 days for adverse event monitoring (serious adverse events will be collected for 90 days after the end of treatment). Subjects who discontinue for reasons other than progressive disease will have

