9. TRIAL FLOW CHART

9.1 Study Flow Chart (Table 4: Trial Flow Chart)

Procedure	Pre- Treatment (within 28 days of starting)	Cycle 1, Day 1 week 1	Cycle 1, Day 2-3	Cycle 2, Day 22	q 3 WK cycles	q6 WK cycles x 2 yr or until progression	q 3 months (Rad Onc)	q 6 months
Initial Screening	X							
Informed Consent	X							
Inclusion/Exclusion	X							
Prior and Concomitant Medication	X							
Full Physical Examination	X			X				
Review of Systems	X			X		X	X	X
Vital Signs	X	X		X		X	X	X
Weight	X	X		X		X	X	X
ECOG Performance Status	X	X		X		X	X	X
HBcAb, HepC Ab	X							
*Bone Marrow Biopsy	X							X (clinical indication)
PET/CT	X						X	
Adverse effects Assessment	X			X	X (Pembro)	X	X	X
Labs								
Baseline Labs *	X							
Myeloma Labs *, LDH, ESR				X		X		
T3, FT4, TSH	X						X	
Pregnancy Test- urine or ser	X						X	
Urinanalysis	X						X	
uric acid, mg, phos, Coags (PTT,	X							
Correlative Biomarkers								
Serum markers (collect)	X	X (pre-RT)	X (Pre-PD1)	X (pre-PD1)		X (3,6 mo) (Pre-PD1)		
ExtraOssseous/Ossseous Biopsy* (clinical indication)								
Treatment								
*Pembrolizumab 200 mg IV			X	X	X			
RT (8 Gy/1fx)		X						
Survival Analysis								X
IMWG Assessment*	X						X	
CTCAE Toxicity*					X	X		

* EOS = end of study (at progression, or when patient stops being treated on the trial)

* Pembrolizumab 200 mg IV q3wk should be given for at least 2 yr and/or until progression.

* Baseline labs = CBC with Diff, CMP, calcium, Albumin, Serum Protein analysis, Quantitative Immunoglobulin, Serum Immunofixation (SIFE), 24 hr urine total protein, Urine Immune-Fixation, Serum Free Light Chain;

*Bone Marrow Biopsy (with IHC, flow, cytogenetics, FISH);

*Whole Body PET/CT every 3 months (as long as insurance approves);

*Biopsy of Osseous or extra-osseous site (if clinically indicated at baseline);

*Myeloma labs: (CBC with diff, CMP, Calcium, Quantitative Immunoglobulin, M-Protein (serum and Urine), Serum Free Light Chain;

* IMWG Assessment = Done at least during 1st month and every 3 months, or as clinically indicated;

*CTCAE Toxicity at the radiated site once at 3 months, 6 months, and 12 months;

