10. TRIAL PROCEDURES

Trial Procedures

The Trial Flow Chart – Section 9.0 summarizes the trial procedures to be performed at each visit. Individual trial procedures are described in detail below. It may be necessary to perform these procedures at unscheduled time points, if deemed clinically necessary by the investigator, and within standard of care.

Furthermore, additional evaluations/testing may be deemed necessary by the Sponsor and/or Merck for reasons related to subject safety. In some cases, such evaluation/testing may be potentially sensitive in nature (e.g., HIV, Hepatitis C, etc.), and thus local regulations may require that additional informed consent be obtained from the subject. In these cases, such evaluations/testing will be performed in accordance with those regulations.

Informed Consent

The Investigator must obtain documented consent from each potential subject prior to participating in a clinical trial.

General Informed Consent

Consent must be documented by the subject's dated signature or by the subject's legally acceptable representative's dated signature on a consent form along with the dated signature of the person conducting the consent discussion.

A copy of the signed and dated consent form should be given to the subject before participation in the trial.

The initial informed consent form, any subsequent revised written informed consent form and any written information provided to the subject must receive the IRB/ERC's approval/favorable opinion in advance of use. The subject or his/her legally acceptable representative should be informed in a timely manner if new information becomes available that may be relevant to the subject's willingness to continue participation in the trial. The communication of this information will be provided and documented via a revised consent form or addendum to the original consent form that captures the subject's dated signature or by the subject's legally acceptable representative's dated signature.

Specifics about a trial and the trial population will be added to the consent form template at the protocol level.

The informed consent will adhere to IRB/ERC requirements, applicable laws and regulations and Sponsor requirements.

Inclusion/Exclusion Criteria

All inclusion and exclusion criteria will be reviewed by the investigator or qualified designee to ensure that the subject qualifies for the trial.

Medical History

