Follow-up Visits for Patients Who Undergo Allogeneic Transplant:

Patients who undergo allogeneic transplant will be monitored for adverse events. For subjects who have an allogeneic SCT within 24 months of last study treatment, transplant parameters will be collected and specific events will be collected for 18 months from the date of the allogeneic transplant to include graft-versus-host-disease (acute and/or chronic), veno-occlusive disease, febrile syndrome (a steroid-requiring febrile illness without an infectious cause), and encephalitis, for all grades, and regardless of relationship to study drug. Additional medically important adverse events post-allogeneic SCT may be submitted at the Investigator's discretion. If available and relevant to an event post-allogeneic SCT, concomitant medications and/or laboratory results may also be reported.

Second Course Phase (Retreatment Period)

Subjects who stop pembrolizumab with SD or better may be eligible for up to one year of additional pembrolizumab therapy if they progress after stopping study treatment. This retreatment is termed the Second Course Phase of this study and is only available if the study remains open and the subject meets the following conditions:

- **Either**
 - Stopped initial treatment with pembrolizumab after attaining an investigator-determined confirmed CR according to IMWG, and

- Was treated for at least 24 weeks with pembrolizumab before discontinuing therapy
- Received at least two treatments with pembrolizumab beyond the date when the initial CR was declared

OR

- Had SD, PR or CR and stopped pembrolizumab treatment after 24 months of study therapy for reasons other than disease progression or intolerance

AND

- Experienced an investigator-determined confirmed disease progression after stopping their initial treatment with pembrolizumab
- Did not receive any anti-cancer treatment since the last dose of pembrolizumab
- Has a performance status of 0 or 1 on the ECOG Performance Scale
- Demonstrates adequate organ function
- Female subject of childbearing potential should have a negative serum or urine pregnancy test within 72 hours prior to receiving retreatment with study medication.

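### Item 9 sets two different limits for the pregnancy test in women of childbearing potential: 72 hours in Section 2 and 2 weeks in Appendix VI

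*Combined protocol and SAP*

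**What the plan says.** Item 9 of the inclusion criteria appears in Section 2 (under Trial Schema) and again in Appendix VI. In both places it opens with the same line, which asks female subjects for a negative urine test within 2 weeks and names no event from which the 2 weeks are counted. A sentence on women of childbearing potential follows, and here the copies differ:

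- Section 2: the test must fall "within 72 hours prior to receiving the first dose of study medication".
- Appendix VI: a "negative urine or serum pregnancy within 2 weeks prior to receiving the first dose of study medication".

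Other text that bears on the point:

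- Section 10, Second Course Phase, sets the limit for retreatment "within 72 hours prior to receiving retreatment with study medication".
- Section 1 gives the order of treatment on cycle 1 as "radiotherapy (8 Gy/1fx) to an extra-osseous or osseous myeloma site followed by pembrolizumab". The radiotherapy is on Day 1. Section 5 states "Trial treatment should be administered on Day 2 or 3 and then every 3 weeks +/- 7 days after that".
- Section 7, in the note to discontinuation item 16, says that "24 months of study medication is calculated from the date of first dose". The item itself concerns pembrolizumab.
- Section 9.1, Table 4, has a row "Pregnancy Test- urine or ser" marked under Pre-Treatment and every 3 months, with no mark at the Day 2-3 infusion.
- Section 10 states: "All inclusion and exclusion criteria will be reviewed by the investigator or qualified designee to ensure that the subject qualifies for the trial".

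**The concern.** One eligibility criterion carries two limits, both in current text, with no rule of precedence. Staff who check eligibility from Appendix VI would apply 2 weeks; staff who use Section 2 would apply 72 hours. The same woman could be recorded as eligible or as a protocol deviation, depending on the page consulted.

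What is at stake is safety. Exclusion 12 bars pregnant patients. Inclusion item 7 in Section 2 allows radiation to any bony part with documented lytic disease, so a pelvic field is not ruled out. A single 8 Gy fraction cannot be withdrawn if a pregnancy is found afterwards. An older negative test leaves more time for a pregnancy that it could not have detected.

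**Working it through.** **Inputs**

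- Limit in Section 2, item 9: 72 h before the first dose of study medication.
- Limit in Appendix VI, item 9: 2 weeks = 14 × 24 = 336 h before the same event.
- Radiotherapy: Day 1 (Section 1), taken as hour 0.
- First pembrolizumab: Day 2 or 3 (Sections 1 and 5), so +24 h or +48 h if both treatments are given at the same clock time. That clock time is an assumption.
- Study medication is read as pembrolizumab. The term is never formally defined; the reading rests on its use in Section 7 (item 16) and in Section 10 (Second Course Phase).

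**Age of the oldest qualifying test at radiotherapy, if taken before it**

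Formula: limit minus the interval from radiotherapy to first pembrolizumab.

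| Rule | Drug on Day 2 | Drug on Day 3 |
|---|---|---|
| Appendix VI | 336 − 24 = 312 h (13 days) | 336 − 48 = 288 h (12 days) |
| Section 2 | 72 − 24 = 48 h | 72 − 48 = 24 h |
| Difference | 312 − 48 = 264 h (11 days) | 288 − 24 = 264 h (11 days) |

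The difference does not depend on how study medication is read. If it included the Day 1 fraction, both limits would count from Day 1 and would still differ by 336 − 72 = 264 h, or 11 days.

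**Where the two lists give opposite answers**

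A test taken more than 48 h and up to 12 days before radiotherapy passes Appendix VI and fails Section 2 whichever day the drug is given.

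**Do other windows settle it?**

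No. Three further windows cover a pregnancy test:

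- the baseline work-up in Section 2, 28 ± 14 days before enrollment;
- the Pre-Treatment column of Table 4, 28 days;
- the screening laboratory tests in Section 10 (Table 5), 14 ± 7 days before first treatment.

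These are general screening windows and, like item 9's opening line, longer than 72 h. Only the retreatment rule points to one of the two limits, and it points to 72 h.

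**One test time that meets the 72-hour limit on either dosing day**

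A test within 24 h before radiotherapy is at most 24 + 24 = 48 h old at a Day 2 infusion and 24 + 48 = 72 h old at a Day 3 infusion. It meets the limit in both cases and comes before the fraction.

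**The case against.** The best reply is that this is a copying slip with little practical effect. Appendix VI looks like an abridged copy: it also lacks exclusions 16 and 17 and some of the detail in items 4 and 7. Nothing shows that staff would work from it alone. A test that meets 72 hours satisfies every other window in the protocol, so a careful reader who applies both lists ends at 72 hours. Section 7 adds contraception requirements. The trial enrolls 24 patients, the number of women of childbearing potential is not given, and no endpoint or estimate depends on the rule. All of this stands, and it keeps the point minor. It does not remove the contradiction, because no text tells a reader to apply the stricter list.

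A reader might infer something stronger: that the whole of item 9 is tied to the wrong event, since the limit counts back from pembrolizumab and not from Day 1 radiotherapy, and so the plan lets a woman be irradiated untested. The documents do not support that. Item 9's opening line names no reference event at all, so only the sentence on women of childbearing potential counts back from the drug. Table 4 marks the test, and the review of eligibility, in the Pre-Treatment column. Section 10 has the criteria reviewed to confirm that the subject qualifies, and exclusion 12 applies from screening. A test is plainly meant to precede radiotherapy. What is left is narrow: the literal wording would accept a repeat test taken after the fraction, for which a short clarification is enough.

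A reader might also conclude that the limit should be moved to 72 hours before radiotherapy. That would be looser than Section 2. For a test taken before the fraction, it allows 72 h at radiotherapy against 48 h or 24 h now, which is 24 to 48 h more. The test could then be 72 + 24 = 96 h or 72 + 48 = 120 h old at first pembrolizumab, which breaks the existing limit.

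**Conclusion.** The contradiction is real. For women of childbearing potential the two copies of item 9 differ by 11 days. If Appendix VI is followed as written, a negative test 12 to 13 days old at an irreversible fraction qualifies. The 72-hour limit is probably the intended one, because the retreatment rule repeats it. That is an inference; the text does not say so.

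The 11-day difference holds however study medication is read. The ages at radiotherapy rest on reading it as pembrolizumab and on equal clock times for the two treatments.

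Severity is minor. The point concerns consistency of eligibility and patient safety; no sample size, endpoint or analysis is affected. The lack of an explicit link to Day 1 radiotherapy is a wording clarification and not a second defect of equal weight.

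**What to change.** 1. In Appendix VI, item 9, in the sentence on women of childbearing potential, replace 2 weeks with 72 hours. Keep the 72-hour limit before first pembrolizumab in Section 2.
2. In both lists, add that this test must be done and be negative before Day 1 radiotherapy. A note can say that a test within 24 hours before radiotherapy meets the limit whether the drug is given on Day 2 or Day 3.
3. In the same sentence, state that for these women this limit overrides item 9's 2-week opening line and the general screening windows.

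The retreatment rule needs no change, since it involves pembrolizumab only.

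With this wording, the qualifying test is at most 48 h (drug on Day 2) or 24 h (drug on Day 3) old at radiotherapy. That is 11 days more recent than Appendix VI now allows. The cost is a wording edit to item 9 in each of the two lists, and an occasional repeat urine test for a woman whose screening test is too old.
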